9 CHANGES TO PLANNED PROTOCOL ANALYSIS

1. The control of false discovery rate (FDR) excluded because it was planned for the secondary (not primary) endpoints and this is a phase 2 study.
2. For the 4th secondary endpoint: <The changes from baseline at Weeks 5, 9, 13, 15, 20 and 24 in the SIB total score for subjects with baseline MMSE-2 scores of 10-14 and 15-18> the list of visits changed from Weeks 9, 15, 20 and 24 to Weeks 9, 20, 24 and 30.
3. For efficacy analysis the GEE models replaced with MMRM models as more suitable approach for analysis of longitudinal data in neurology studies.

QMD Ref: Worldwide-TMP-ST-005-7.0 Effective: 12Aug2019	Governing QMD: Worldwide-SOP-ST-001
Confidentiality Statement	
This document is the property of Worldwide Clinical Trials Inc. and may not be duplicated, copied, altered or removed from company without prior approval from Worldwide Quality Assurance or in compliance with Worldwide Standard Operating Procedures.	

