9.4 Analysis of Primary Efficacy Endpoint

The treatment difference in the primary efficacy endpoint of total SIB scores from baseline at Week 28 will be determined from a regression model that utilize SIB values taken at Weeks 0, 5, 9, 13, 15, 20, 24, 28 and 30. As SIB is a continuous outcome measure, a regression model will be used to estimate the treatment difference in mean SIB from baseline at Week 28. Both linear and non-linear terms will be considered in these regression models. Since correlation of SIB measures over time within a patient will be present, regression coefficients will be estimated using the generalized estimating equations (GEE) methodology.¹⁸ GEE regression models are used to appropriately estimate the population average effects from a sample of individuals when the correlations of SIB measures within individuals are unknown. The GEE method accounts for the correlation structure in the model. However, the estimates of model coefficients and their standard errors models are unbiased even if the working correlation model is incorrectly specified. The primary analysis will be conducted on FAS population. The PP and CAS populations will be used as supportive analyses. All statistical tests for efficacy will be two-sided tests, with $\alpha=0.05$.

Based on the review of patients not treated with memantine in the NTRP 101-203 clinical trial, the expected number of patients who will drop out of the study prematurely will not be significant. However, missingness will be accounted for using weighted GEE methods.¹⁹ The GEE regression models will be carried out in SAS/STAT PROC GEE version 13.2. This SAS procedure will allow for implementation of weighted GEE methodology that can account for data missing a random. One additional patient may be randomized for each patient who discontinues the study prior to the primary endpoint (Week 28, Day 196).

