9.5 Secondary Efficacy Endpoints

Multiple comparisons arising from the listed secondary outcomes will be controlled by using the false discovery rate. This procedure will allow control of the type I error rate over the set of secondary outcomes that is less stringent than controlling for multiple comparisons using a familywise error rate (e.g. Bonferroni correction).

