6.11 Efficacy Analyses

All statistical tests will be performed using a two-tailed 5% overall significance level, unless otherwise stated. All comparisons between treatments will be reported with 95% confidence intervals for the difference.

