6.11.4.1 SIB total score at the Week 42 follow-up visit

This endpoint will be analyzed using an Analysis of Covariance (ANCOVA) model with SIB score at Week 42 as dependent variable; treatment group as factor, and baseline SIB total score, baseline MMSE-2 score, age and gender as covariates.

6.11.4.2 The change from baseline in SIB total score at Week 13

This endpoint will be analyzed using the same ANCOVA model as described in Section 6.11.6.1.

6.11.4.3 SIB total scores from baseline at Weeks 9, 20, 24 and 30

This endpoint will be analyzed using the same MMRM model as described in Section 6.11.2 with corrections for obtaining results on corresponding visits.

6.11.4.4 SIB total scores from baseline at Weeks 9, 20, 24 and 30 for subjects with baseline MMSE-2 scores of 10-14 and 15-18

This endpoint will be analyzed using the same MMRM model as described in Section 6.11.2 with additional fixed effect for grouped baseline MMSE-2 scores (10-14 and 15-18) and corrections for obtaining results on corresponding visits.

QMD Ref: Worldwide-TMP-ST-005-7.0 Effective: 12Aug2019	Governing QMD: Worldwide-SOP-ST-001
Confidentiality Statement	
This document is the property of Worldwide Clinical Trials Inc. and may not be duplicated, copied, altered or removed from company without prior approval from Worldwide Quality Assurance or in compliance with Worldwide Standard Operating Procedures.	

Worldwide Clinical Trials Controlled Quality Management Document		
 WORLDWIDE CLINICAL TRIALS	Sponsor:	Synaptogenix, Inc.
	Protocol Number:	NTRP-101-204
STATISTICAL ANALYSIS PLAN. PHASE 2-3-4		

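### The SAP drops the protocol's false-discovery-rate control over the secondary SIB endpoints, puts nothing in its place, and does not label the secondary p-values as nominal

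*SAP*

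**What the plan says.** Protocol 9.5: "Multiple comparisons arising from the listed secondary outcomes will be controlled by using the false discovery rate". The same paragraph explains that FDR was preferred because it is less stringent than a familywise correction such as Bonferroni.

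SAP 9 item 1 removes this control: "The control of false discovery rate (FDR) excluded because it was planned for the secondary (not primary) endpoints". Its full reason has two parts: "it was planned for the secondary (not primary) endpoints and this is a phase 2 study".

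SAP 6.11 then sets the level for every efficacy test: "All statistical tests will be performed using a two-tailed 5% overall significance level, unless otherwise stated". No procedure is given that would make the level hold across tests. SAP 6.11.4 contains no testing order, alpha allocation or statement that the secondary p-values are descriptive.

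Three other places matter:

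- The synopsis, under Statistical Considerations, makes superiority on the primary **and** secondary SIB endpoints the primary objective for efficacy.
- The protocol title calls the trial a confirmatory phase 2 study. Protocol 4.0 calls it exploratory, and the title in SAP 1 omits the word confirmatory.
- Protocol 9 and SAP 6 both give the SAP precedence. Protocol 9 adds that major modifications will also appear in a protocol amendment.

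**The concern.** The two documents disagree, and the SAP's reason does not explain why the rule should go. Applying to secondary endpoints was the purpose of the rule, and the trial was already phase 2 when the rule was written.

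What is at stake is how the secondary results may be read. The efficacy objective includes them, they cover several visits, two MMSE-2 groups and slopes, and each would be tested at 5% without protection. If the primary test fails, one nominally significant visit or subgroup could be presented as evidence of benefit. The protocol's account of NTRP101-202 (2.1.2.4) shows how that can happen. It describes many results for single visits, analysis sets and covariate models as significant at a one-sided 0.10 level. Protocol 2.1.2.6 states that nothing beyond Week 5 was met in the full analysis set.

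**Working it through.** The plan gives no test count or error rate for the secondary family, so there is no stated figure to reproduce. Its only calculated design figure is the power of the primary analysis, which does not bear on this point.

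**Step 1. Count the between-arm secondary comparisons in SAP 6.11.4.**

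- 6.11.4.1, Week 42: 1
- 6.11.4.2, Week 13: 1
- 6.11.4.3, Weeks 9, 20, 24 and 30: 4
- 6.11.4.4, the same weeks with MMSE-2 groups: 4 or 8. The text adds MMSE-2 group only as a fixed effect. Read literally, this gives four further overall contrasts that nearly duplicate 6.11.4.3. If each group is tested, as the endpoint's title implies, it gives 4 × 2 = 8.
- 6.11.4.5, slope difference: 1, or 2 if both the absolute and change scales are counted. The slopes of each arm against zero are not treatment comparisons and are left out.

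Literal reading: 1 + 1 + 4 + 4 + 1 = 11. By MMSE-2 group: 1 + 1 + 4 + 8 = 14 without slopes, and 14 + 2 = 16 with both slope differences.

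**Step 2. Check the visit lists.** They conflict, so the count is not fixed.

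- SAP 3.2 lists Weeks 5, 9, 15, 20 and 24 overall, and six weeks including Week 13 for the MMSE-2 groups. That gives 1 + 1 + 5 + 12 = 19 before slopes.
- Protocol 4.3.3 lists Weeks 9, 13, 20, 24 and 30 for the groups. That gives 1 + 1 + 4 + 10 = 16 before slopes.
- The heading of Protocol 9.5.4 lists Weeks 5, 9, 15, 20 and 24. Its text lists Weeks 9, 20, 24 and 30 and then refers to five time points.
- SAP 9 item 2 adopts Weeks 9, 20, 24 and 30 for the group endpoint, but SAP 3.2 was not updated.

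**Step 3. Expected false positives with no effect.** This is 0.05 × k whatever the correlation: 0.55 for 11 tests, 0.70 for 14 and 0.80 for 16.

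**Step 4. Chance of at least one p<0.05.** If tests were independent it would be 1 − 0.95^k, which is 51% for 14, 56% for 16 and 64% for 20 (20 includes the single-arm slopes). These tests are not independent. The primary model in SAP 6.11.2 treats time as continuous, so the Week 9, 20, 24 and 30 contrasts all come from two treatment parameters. The independence figures should not be quoted as the error rate.

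The check was therefore made by simulation: 6,000 trials with no effect, 50 per arm, SD 5.3 (from SAP 4), complete data, two equal MMSE-2 groups, and half the subjects with Week 42. Visit contrasts were taken from a straight line in time, adjusted for baseline, as a simplified stand-in for the SAP's mixed model. The within-person correlation was 0.5 (from SAP 4), or 0.7 with a random-slope SD of 0.15 (assumed).

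| Family | Correlation 0.5 | Correlation 0.7 with random slopes |
|---|---|---|
| 11 tests (literal) | about 21% | about 18% |
| 14 tests | about 28% | about 24% |
| 16 tests | about 32% | about 27% |

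The simulation error is about 0.6 percentage points (√(0.32 × 0.68 / 6,000) = 0.006), so the overall range is roughly 18% to 33%.

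**Step 5. Restore Benjamini-Hochberg at 5%.** Over the same families the chance of any false secondary finding falls to about 3% to 5%. When no effect exists, the false discovery rate equals the chance of any false finding, so this is the expected result.

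**The case against.** The strongest case for the SAP has four parts.

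- **Phase 2 secondary tests are often left unadjusted.** This is defensible when they are labelled nominal, and Protocol 4.0 does call the study exploratory. The argument stands as a principle, but the SAP applies no such label and keeps a 5% overall level.
- **The change is disclosed and the protocol allows for it.** The SAP has precedence and says it was approved before complete unmasking. Whether dropping FDR is a major modification that needs an amendment is a judgement. A reader might infer a breach of the protocol or a change made after seeing results. The documents support neither.
- **The inflation is easily overstated.** A reader might infer a false-positive chance of 51% to 64%. That needs independent tests, and its upper end also counts four single-arm slopes against zero. In a progressive disease, a non-zero slope is not a false positive for drug effect. This objection stands, and the simulated range replaces those figures.
- **The history of NTRP101-202 is not part of this plan.** That trial used a different error level, and NTRP101-203 is openly reported as showing no significant efficacy difference. The history shows a risk of selective reading and is not evidence of a fault in this SAP.

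**Conclusion.** The point holds. The SAP removes a pre-specified rule on two grounds that both already applied when the rule was written. It leaves about 11 to 16 correlated between-arm comparisons at an unadjusted 5%, under wording that claims an overall level. With no true effect, the chance of at least one nominally significant secondary result is roughly 18% to 33%, against no more than about 5% with the protocol's rule.

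These figures rest on the reading of SAP 6.11.4.4, complete data, the assumed share of subjects with Week 42, the two correlation settings and a simplified model. Other choices would move the figures, but every family and setting tried stayed well above 5%.

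A reader might also infer that the primary conclusion is compromised. It is not, because the Week 28 comparison is a single named test whose type I error does not depend on how the secondary endpoints are handled.

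**What to change.** **Preferred**

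1. Delete SAP 9 item 1.
2. Reconcile the visit lists in SAP 3.2, SAP 6.11.4, Protocol 4.3.3 and Protocol 9.5.4, and state whether SAP 6.11.4.4 is tested within each MMSE-2 group.
3. Name one family of between-arm secondary comparisons, excluding single-arm slopes against zero.
4. Apply Benjamini-Hochberg at 5% to that family and report raw and adjusted p-values side by side.

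**Minimum, if the sponsor keeps the deletion**

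1. State in the SAP that all secondary p-values are nominal and support no efficacy claim.
2. Correct the word overall in SAP 6.11.
3. Amend Protocol 9.5 to match.

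**Cost.** The preferred route needs one programming step (for example PROC MULTTEST), the work of settling the visit lists, and SAP wording. The downside is that some nominally significant secondary results will no longer be flagged. Raw p-values stay visible and the primary analysis does not change.

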11 LIST OF TABLES, FIGURES AND LISTINGS

Table Number	Table Title	Validation Method	Shell Number (if repeat)
14.1	Demographics Data		
14.1.1	Disposition		
14.1.1.1	Subject Disposition, Analysis Sets	IP	
14.1.1.2	Screen Failures	IP	
14.1.1.3	Inclusion/Exclusion Criteria not met, Screen Failures	IP	
14.1.1.4	Subject Disposition, Early Withdrawal	IP	
14.1.1.5	Safety Analysis Set by Site	IP	
14.1.1.6	Subject Visits	IP	
14.1.1.7	Protocol Deviations	IP	
14.1.2	Demographics		
14.1.2.1	Demographics. Safety Analysis Set	IP	
14.1.2.2	Demographics. Full Analysis Set	IP	
14.1.3	Baseline Characteristics		
14.1.3.1	Prior Medical History. Safety Analysis Set	IP	
14.1.3.2	Prior Medical History. Full Analysis Set	IP	
14.1.3.3	Ongoing Medical History. Safety Analysis Set	IP	
14.1.3.4	Ongoing Medical History. Full Analysis Set	IP	
14.2	Efficacy Data		
14.2.1	Primary Efficacy Endpoint		
14.2.1.1	Severe Impairment Battery. Full Analysis Set	Stat IP	
14.2.1.2	Severe Impairment Battery. Per-Protocol Analysis Set	Stat IP	
14.2.1.3	Severe Impairment Battery. Completers Analysis Set	Stat IP	

QMD Ref: Worldwide-TMP-ST-005-7.0 Effective: 12Aug2019	Governing QMD: Worldwide-SOP-ST-001
Confidentiality Statement	
This document is the property of Worldwide Clinical Trials Inc. and may not be duplicated, copied, altered or removed from company without prior approval from Worldwide Quality Assurance or in compliance with Worldwide Standard Operating Procedures.	

Worldwide Clinical Trials Controlled Quality Management Document

**WORLDWIDE
CLINICAL TRIALS**

Sponsor:

Synaptogenix, Inc.

Protocol Number:

NTRP-101-204

STATISTICAL ANALYSIS PLAN. PHASE 2-3-4

Table Number	Table Title	Validation Method	Shell Number (if repeat)
14.2.1.4	Mixed Model with Repeated Measures Analysis of Change from Baseline at week 28 in Severe Impairment Battery. Main Analysis	Stat IP	
14.2.1.5	Mixed Model with Repeated Measures Analysis of Change from Baseline at week 28 in Severe Impairment Battery. Sensitivity Analysis: Visit included as categorical predictor	Stat IP	
14.2.1.6	Mixed Model with Repeated Measures Analysis of Change from Baseline at week 28 in Severe Impairment Battery. Supportive Analysis: Best Case Approach	Stat IP	
14.2.1.7	Mixed Model with Repeated Measures Analysis of Change from Baseline at week 28 in Severe Impairment Battery. Supportive Analysis: Worst Case Approach	Stat IP	
14.2.1.8	Mixed Model with Repeated Measures Analysis of Change from Baseline at week 28 in Severe Impairment Battery. Supportive Analysis: Per-Protocol Analysis Set	Stat IP	
14.2.1.9	Mixed Model with Repeated Measures Analysis of Change from Baseline at week 28 in Severe Impairment Battery. Supportive Analysis: Completers Analysis Set	Stat IP	
14.2.2	Secondary Efficacy Endpoints		
14.2.2.1	Analysis of Covariance model for Severe Impairment Battery at Week 42 follow-up visit	Stat IP	
14.2.2.2	Analysis of Covariance model for Change from Baseline of Severe Impairment Battery at Week 13	Stat IP	
14.2.2.3	Mixed Model with Repeated Measures Analysis of Changes from Baseline at weeks 9, 20, 24 and 30 in Severe Impairment Battery	Stat IP	
14.2.2.4	Mixed Model with Repeated Measures Analysis of Changes from Baseline at weeks 9, 20, 24 and 30 in Severe Impairment Battery for subjects with baseline MMSE-2 scores of 10-14 and 15-18	Stat IP	
14.2.2.5	Individual subject's trends of SIB over time	Stat IP	
14.2.2.6	Individual subject's trends of SIB changes from baseline over time	Stat IP	
14.2.3	Exploratory Endpoints		

QMD Ref: Worldwide-TMP-ST-005-7.0 Effective: 12Aug2019

Governing QMD: Worldwide-SOP-ST-001

Confidentiality Statement

This document is the property of Worldwide Clinical Trials Inc. and may not be duplicated, copied, altered or removed from company without prior approval from Worldwide Quality Assurance or in compliance with Worldwide Standard Operating Procedures.

Worldwide Clinical Trials Controlled Quality Management Document

**WORLDWIDE
CLINICAL TRIALS**

Sponsor:

Synaptogenix, Inc.

Protocol Number:

NTRP-101-204

STATISTICAL ANALYSIS PLAN. PHASE 2-3-4

Table Number	Table Title	Validation Method	Shell Number (if repeat)
14.2.3.1	Mixed Model with Repeated Measures Analysis of Change from Baseline at weeks 13 and 42 in Alzheimer’s Disease Cooperative Study – Activities of Daily Living - Severe Impairment Version	Stat IP	
14.2.3.2	Mixed Model with Repeated Measures Analysis of Change from Baseline at weeks 13 and 42 in Mini Mental State Examination, 2nd edition	Stat IP	
14.2.3.3	Mixed Model with Repeated Measures Analysis of Change from Baseline at weeks 13 and 42 in Neuropsychiatric Inventory	Stat IP	
14.3	Safety Data		
14.3.1	Displays of Adverse Events		
14.3.1.1	Overview of Adverse Events	IP	
14.3.1.2	Treatment Emergent Adverse Events	IP	
14.3.1.3	Patients with Treatment Emergent Adverse Events by Maximal Severity	IP	
14.3.1.4	Patients with Treatment Emergent Adverse Events by Maximal Relationship to Study Treatment	IP	
14.3.1.5	Serious Treatment Emergent Adverse Events	IP	
14.3.1.6	Treatment Emergent Adverse Events Resulting in Discontinuation of Study Treatment	IP	
14.3.1.7	Patients with Treatment Emergent Adverse Events Resulting in Discontinuation of Study Treatment by Maximal Relationship to Study Treatment	IP	
14.3.1.8	Patients with Treatment Emergent Adverse Events that Lead to Study Discontinuation by Maximal Relationship to Study Treatment	IP	
14.3.1.9	Patients with Serious Treatment Emergent Adverse Events by Maximal Relationship to Study Treatment	IP	
14.3.1.10	Treatment Emergent Adverse Events of Special Interest	IP	
14.3.4	Abnormal Laboratory Values		
14.3.4.1	Hematology, Measured Values and Changes from Baseline by Visit	IP	
14.3.4.2	Hematology, Shifts from Baseline to Post-Baseline Visits	IP	
14.3.4.3	Clinical chemistry, Measured Values and Changes from Baseline by Visit	IP	

QMD Ref: Worldwide-TMP-ST-005-7.0 Effective: 12Aug2019

Governing QMD: Worldwide-SOP-ST-001

Confidentiality Statement

This document is the property of Worldwide Clinical Trials Inc. and may not be duplicated, copied, altered or removed from company without prior approval from Worldwide Quality Assurance or in compliance with Worldwide Standard Operating Procedures.

Worldwide Clinical Trials Controlled Quality Management Document

**WORLDWIDE
CLINICAL TRIALS**

Sponsor:

Synaptogenix, Inc.

Protocol Number:

NTRP-101-204

STATISTICAL ANALYSIS PLAN. PHASE 2-3-4

Table Number	Table Title	Validation Method	Shell Number (if repeat)
14.3.4.4	Clinical chemistry, Shifts from Baseline to Post-Baseline Visits	IP	
14.3.5	Extent of Exposure, Dosage Information and Compliance		
14.3.5.1	Exposure	IP	
14.3.6	Vital Signs and Physical Examination		
14.3.6.1	Vital Signs, Measured Values and Changes from Baseline by Visit	IP	
14.3.6.2	Weight and BMI, Measured Values and Changes from Baseline by Visit	IP	
14.3.6.3	Physical Examination	IP	
14.3.7	Other Safety		
14.3.7.1	Electrocardiogram, Measured Values and Changes from Baseline by Visit	IP	
14.3.7.2	Electrocardiogram, Shift in Overall interpretation from Baseline to Post-Baseline Visits	IP	
14.3.7.3	Columbia-Suicide Severity Rating Scale (C-SSRS) at Screening	IP	
14.3.7.4	Columbia-Suicide Severity Rating Scale (C-SSRS) at Post-baseline Visits	IP	
14.3.8	Concomitant Medication		
14.3.8.1	Prior Medications. Safety Analysis Set	IP	
14.3.8.2	Prior Medications. Full Analysis Set	IP	
14.3.8.3	Concomitant Medications. Safety Analysis Set	IP	
14.3.8.4	Concomitant Medications. Full Analysis Set	IP	

QMD Ref: Worldwide-TMP-ST-005-7.0 Effective: 12Aug2019

Governing QMD: Worldwide-SOP-ST-001

Confidentiality Statement

This document is the property of Worldwide Clinical Trials Inc. and may not be duplicated, copied, altered or removed from company without prior approval from Worldwide Quality Assurance or in compliance with Worldwide Standard Operating Procedures.

REF: Worldwide-TMP-QA-001F-1.3

Page 32 of 35

Worldwide Clinical Trials Controlled Quality Management Document		
 WORLDWIDE CLINICAL TRIALS	Sponsor:	Synaptogenix, Inc.
	Protocol Number:	NTRP-101-204
STATISTICAL ANALYSIS PLAN. PHASE 2-3-4		

Figure Number	Figure Title	Validation Method	Shell Number (if repeat)
14.2.1	Primary Efficacy Endpoint		
14.2.1.1	Mean Values with 95% Confidence Intervals of Severe Impairment Battery. Full Analysis Set	IP	
14.2.1.2	Mean Values with 95% Confidence Intervals of Severe Impairment Battery. Per-Protocol Analysis Set	IP	14.2.1.1
14.2.1.3	Mean Values with 95% Confidence Intervals of Severe Impairment Battery. Completers Analysis Set	IP	14.2.1.1
14.2.1.4	LS Mean Values with 95% Confidence Intervals of Change from Baseline in Severe Impairment Battery. Main Analysis	IP	14.2.1.1
14.2.1.5	LS Mean Values with 95% Confidence Intervals of Change from Baseline in Severe Impairment Battery. Sensitivity Analysis	IP	14.2.1.1

QMD Ref: Worldwide-TMP-ST-005-7.0 Effective: 12Aug2019	Governing QMD: Worldwide-SOP-ST-001
Confidentiality Statement	
This document is the property of Worldwide Clinical Trials Inc. and may not be duplicated, copied, altered or removed from company without prior approval from Worldwide Quality Assurance or in compliance with Worldwide Standard Operating Procedures.	

Worldwide Clinical Trials Controlled Quality Management Document

**WORLDWIDE
CLINICAL TRIALS**

Sponsor:

Synaptogenix, Inc.

Protocol Number:

NTRP-101-204

STATISTICAL ANALYSIS PLAN. PHASE 2-3-4

Listing Number	Listing Title	Validation Method	Shell Number (if repeat)
16.2	Subject Data Listings		
16.2.1	Discontinued Subjects		
16.2.1.1	Early Withdrawals	IP	
16.2.1.2	Subject Visits	IP	
16.2.1.3	Screen Failures		
16.2.1.4	Eligibility Criteria		
16.2.2	Protocol Deviations		
16.2.2.1	Protocol Deviations	IP	
16.2.3	Subjects Excluded from The Efficacy Analyses		
16.2.3.1	Analysis Sets	IP	
16.2.4	Demographic Data		
16.2.4.1	Demographic Data	IP	
16.2.4.2	Prior and Ongoing Medical History	IP	
16.2.4.3	Prior and Concomitant Medications	IP	
16.2.4.4	Non-Pharmacological Procedures	IP	
16.2.4.5	Rosen-modified Hachinski Ischemic score	IP	
16.2.5	Compliance		
16.2.5.1	Exposure	IP	
16.2.6	Individual Efficacy Response Data		
16.2.6.1	Severe Impairment Battery. Questions 1-20	IP	
16.2.6.2	Severe Impairment Battery. Questions 21-40	IP	
16.2.6.3	Severe Impairment Battery. Total Scores	IP	
16.2.6.4	Alzheimer Disease Cooperative Study - Activities of Daily Living - Severe Impairment Version	IP	
16.2.6.5	Alzheimer Disease Cooperative Study - Activities of Daily Living - Severe Impairment Version. Total Scores	IP	
16.2.6.6	Mini Mental State Examination Version 2	IP	
16.2.6.7	Mini Mental State Examination Version 2. Total Scores	IP	
16.2.6.8	Neuropsychiatric Inventory	IP	
16.2.6.9	Neuropsychiatric Inventory. Total Scores	IP	
16.2.7	Adverse Event Listings		
16.2.7.1	Pre-Treatment Adverse Events	IP	
16.2.7.2	Treatment Emergent Adverse Events	IP	
16.2.7.3	Serious Treatment Emergent Adverse Events	IP	

QMD Ref: Worldwide-TMP-ST-005-7.0 Effective: 12Aug2019

Governing QMD: Worldwide-SOP-ST-001

Confidentiality Statement

This document is the property of Worldwide Clinical Trials Inc. and may not be duplicated, copied, altered or removed from company without prior approval from Worldwide Quality Assurance or in compliance with Worldwide Standard Operating Procedures.

Worldwide Clinical Trials Controlled Quality Management Document

WORLDWIDE
CLINICAL TRIALS

Sponsor:

Synaptogenix, Inc.

Protocol Number:

NTRP-101-204

STATISTICAL ANALYSIS PLAN. PHASE 2-3-4

Listing Number	Listing Title	Validation Method	Shell Number (if repeat)
16.2.7.4	Treatment Emergent Adverse Events resulting in discontinuation of study treatment	IP	
16.2.7.5	Treatment Emergent Adverse Events with Fatal Outcome	IP	
16.2.8	Individual Laboratory Measurements and Other Safety		
16.2.8.1	Hematology Results	IP	
16.2.8.2	Clinical Chemistry Results	IP	
16.2.8.3	Screening Clinical Chemistry Results	IP	
16.2.8.4	Vital Signs	IP	
16.2.8.5	Temperature	IP	
16.2.8.6	Weight and BMI	IP	
16.2.8.7	Physical Examinations	IP	
16.2.8.8	Electrocardiogram Results	IP	
16.2.8.9	Pregnancy Urine Test	IP	
16.2.8.10	Columbia-Suicide Severity Rating Scale (C-SSRS)	IP	

QMD Ref: Worldwide-TMP-ST-005-7.0 Effective: 12Aug2019

Governing QMD: Worldwide-SOP-ST-001

Confidentiality Statement

